11.2 Secondary Analyses

11.2.1 Secondary Endpoint:

The secondary safety endpoint is to report the severe complication-free rate for the updated e·Sense® catheters. The secondary safety hypothesis is a comparison of the lower bound for the estimate of the success rate to a minimally acceptable target value of 95%:

H_0 : Severe complication-free rate of $\leq 95\%$

versus

H_A : Severe complication-free rate of $> 95\%$

This 1-sided hypothesis will be evaluated by comparing the lower limit of the 95% 1-sided Clopper-Pearson confidence interval to the target value. If the lower limit of the 95% 1-sided

	e·Sense® Clinical Investigation Protocol	CLN-00021-ESNS-PH01-PR-01	Version B
---	---	---------------------------	-----------

Clopper-Pearson confidence interval is greater than the target value, the null hypothesis will be rejected, and it will be concluded that a severe complication-free rate $\leq 95\%$ is inconsistent with the investigation findings. The lower limit of the 95% 1-sided Clopper-Pearson confidence interval is identical to the lower limit of a 2-sided 90% Clopper-Pearson confidence interval, so the 2-sided Clopper-Pearson 90% confidence interval may be calculated for computational ease. In addition, a 1-sided, 1-sample binomial test will be performed to calculate a p-value. $P < 0.05$ will be considered statistically significant.

11.2.2 Sample Size Determination & Power:

The null hypothesis for the secondary safety endpoint is designed to rule out success rates $\leq 95\%$. Based on clinical judgement and previous testing, a true success rate of 100% is assumed.

Power was determined by 10,000 binomial simulations (assuming success rate 100%) for each sample size, and calculation of the proportion of simulations for which the null hypothesis would be rejected based on the lower limit of the 2-sided 90% Clopper-Pearson confidence interval. Analysis of 60 subjects would provide 99% power to rule out a success rate $\leq 95\%$ when the true success rate is assumed to be 100%, based on a 1-sided test with type I error rate of 5%. This study requires a minimum of 60 subjects for adequate power to reject the null hypothesis when the true assumed rate is 100%, however the final sample size will be based on site enrolment capabilities within the project timeline. In addition, the study sponsor will allow up to 65 subjects (5 additional) during the allowable recruitment and project time given the minimum recruitment goals are met. The additional subjects will ensure the desired confidence and reliability levels are met should any data or subjects be excluded from the primary analysis population (See Section 11.5) or if the subject withdraws (See Section 6.6). If the enrolment target is not reached, the exact confidence interval will be calculated for the data available, but no hypothesis test will be conducted.

11.3 Exploratory Analyses

Descriptive statistics will be used to summarize and analyse the results of each of the exploratory endpoints at the completion of the study.

11.3.1 First Exploratory Endpoint:

The first exploratory endpoint is to assess user impressions of the updated e·Sense® catheters compared with their experience using the existing catheters at their site, by evaluating the following subjective measures: ease of use, ease of insertion and removal, ease of securing the catheter, tracing stability (during filling, voiding and UPP where applicable), tracing quality (overall, Pves, Pabd and Pura where applicable), channel subtraction quality, visibility on VUDS (where applicable), instruction for use evaluation, catheter stiffness, sensor location, patient tolerance, and overall usability performance.

The reported value in the usability performance survey will be analysed using proportions of levels and combined proportions of groupings. This includes levels (1 to 5), "Yes and No", "Better, Same or worse" and any other questions related to usability. The results will also be

	e·Sense® Clinical Investigation Protocol	CLN-00021-ESNS-PH01-PR-01	Version B
---	---	---------------------------	-----------

analysed grouped by the site's existing catheter technology (e.g. grouping by water, air, or electronic technology results). Additionally, the results will be plotted over time to observe the trend as the study continues (preferably a line plot with daily responses over time).

11.3.2 Second Exploratory Endpoint

The second exploratory endpoint is to assess subjective subject feedback regarding their discomfort and pain levels.

The reported value in the patient survey will be analysed using proportions of levels and combined proportions of groupings. This includes levels (0 to 10) and "Yes and No".

11.3.3 Third Exploratory Endpoint

The third exploratory endpoint is to assess pre-test resting pressure of the e·Sense® catheters at sitting, standing, and supine patient positions.

11.3.4 Fourth Exploratory Endpoint

The fourth exploratory endpoint is to assess resting pressure of the e·Sense® catheters at the recorded patient position during various points of the UDS test (every 100mL of filling, MCC, and post-void).

11.4 Randomization / Blinding

Randomization and/or blinding is not utilized in this study based on the study design.

11.5 Analysis Population

The primary analysis population to be considered in this study will include enrolled subjects who have been successfully catheterized using the investigational device. Should catheterization fail due to a device deficiency, and/or adverse event, these subjects will still be included in the primary analysis and this information shall be recorded on the subjects' CRF#1 (ESNS-PH01-CRF-01), as well as on the adverse event form (ESNS-PH01-CRF-05), or device deficiency form (ESNS-PH01-CRF-06) as applicable. However, should catheterization fail due to patient factors (i.e. the characteristics of the catheter didn't meet patient anatomical needs, coudé tip required, inappropriate French size), these subjects will be considered as part of the sensitivity analysis population.

All subjects in the primary analysis population will be included in the primary analysis of the hypotheses tests. The sensitivity analysis population will also be analysed as the "intent to treat" population, however results of this population will not dictate success or failure of the study and are meant for comparison purposes only. Data will be analysed as outlined in Section 12.1.

Any subjects who are enrolled but for any reason subsequently withdraw from the study prior to being catheterized with the investigational device, will be excluded from analysis. The justification being they were never touched, and no measurements were made with the investigational device.

	e·Sense® Clinical Investigation Protocol	CLN-00021-ESNS-PH01-PR-01	Version B
---	---	---------------------------	-----------

If any CRFs are found to be incomplete, the study monitor will follow-up as to the reasoning. If for some reason a clinical user is unable to fully complete their questionnaire, the questions they have completed will be included in the analysis. Data will be monitored as the study progresses, refer to Section 6.7 for details pertaining to suspension or premature termination.

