6.4 Recruitment Plans

To satisfy the primary objective, the target enrolment is a minimum of 30 subjects with an attempted UDS study (e·Sense® catheter has made contact with the patient's body). To satisfy the secondary objective, the target enrolment is a minimum 60 subjects with an attempted UDS study (e·Sense® catheter has made contact with the patient's body). In addition, the study sponsor will allow up to 65 subjects (5 additional) during the allowable recruitment and project time given the minimum recruitment goals are met. Please refer to Section 11 for details on sample size determination.

Subjects who are visiting the UDS clinic for their medically indicated UDS test will be approached regarding participation in this study. It is estimated that study-wide recruitment of 60 subjects should take approximately 18 weeks of active recruitment at each site. Recruitment will be monitored by Laborie through scheduled meetings with the site co-ordinator. If the subject signs the informed consent, this will be treated as the point of enrolment.

The minimum number of clinical sites shall be two. The maximum number of sites allowed for this study shall be four. A minimum of 15 subjects per site is required to ensure proper distribution across sites. Once each site has met the minimum recruitment of 15 subjects, the sponsor will be informed. Following this, the site may have the option to continue recruitment until the study-wide maximum is reached, based on the discretion of the sponsor. Additional enrolment following the minimum recruitment goal will be dictated by the final number of sites initiated.

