11.7 Interim Analysis

Once 30 primary analysis population subjects complete the study the primary composite safety and effectiveness analysis will be conducted for regulatory purposes. Once all (60-65) subjects are complete, the secondary endpoint analysis will be performed. In addition, the exploratory endpoints will be assessed and an exploratory analysis of the composite (primary) safety and effectiveness endpoint including all subjects will be performed.

There are currently no criteria for stopping the study early on statistical grounds. Refer to Section 5.3 for details about suspension or premature termination.

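### Section 11.2 names no analysis set for the secondary severe-complication test; the likelier one omits contacted subjects whose catheterization failed for patient factors, and one severe complication among them would reverse the result

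*Combined protocol and SAP*

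**What the plan says.** Section 11.2.1 tests a severe complication-free rate against 95% with a one-sided 95% Clopper-Pearson lower limit. It names no analysis population. Two passages point to the primary analysis population:

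- Section 11.5: "All subjects in the primary analysis population will be included in the primary analysis of the hypotheses tests". The plural takes in the secondary test. This population is the subjects successfully catheterized, plus failures due to a device deficiency and/or an adverse event. But "should catheterization fail due to patient factors" (anatomy, need for a coudé tip, wrong French size), the subject moves to a sensitivity population whose results cannot decide the study outcome.
- Section 11.2.2, on the secondary sample size, justifies the allowance up to 65 as cover "should any data or subjects be excluded from the primary analysis population".

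Other passages point elsewhere or leave it open:

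- Section 6.4: "To satisfy the secondary objective, the target enrolment is a minimum 60 subjects with an attempted UDS study", where attempted means that the catheter touched the patient's body.
- Section 10.2 refers to primary and secondary analysis populations and cites 11.5, which defines only a primary and a sensitivity (intent-to-treat) population.
- Section 11.7: "Once all (60-65) subjects are complete, the secondary endpoint analysis will be performed", with no set named.

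**The concern.** Two statisticians could follow this text and use different denominators for the same safety test. On the likelier reading, some subjects exposed to the device fall outside it. Exposure to the risk begins with instrumentation, not with successful placement: Section 3.6 lists infection and urethral trauma among the risks of urethral instrumentation, and an unsuccessful attempt also involves instrumentation.

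Keeping failures due to an adverse event covers a complication that stops the catheterization. It does not cover one that appears after a failure put down to anatomy or catheter size, such as an event reported at the telephone call in Section 7.5. Nor does 11.5 say how to classify a failure with both kinds of cause. Section 9.2 judges endpoint success by whether the null hypothesis is rejected, so an event shown only in the sensitivity set cannot change that judgement.

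**Working it through.** **Inputs.** Target rate 95%, one-sided alpha 5%, Clopper-Pearson lower limit must exceed 95% (11.2.1). Assumed true rate 100%, n = 60, stated power 99%, cap 65 (11.2.2).

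**Formulas.** For n subjects with no event, the lower limit is L = 0.05^(1/n) and p = 0.95^n. With one event, L is the 5% quantile of a Beta(n−1, 2) distribution and p = 0.95^n + n × 0.05 × 0.95^(n−1).

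**The plan's own figure.** At n = 60 with no event, L = 0.05^(1/60) = 0.9513 and p = 0.95^60 = 0.0461, so the null is rejected. If the true rate is 100%, this outcome is certain and power is 100%, which agrees with the stated 99%. The power statement is not in dispute.

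**Effect of one contacted patient-factor failure with a severe complication, no event elsewhere.**

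| Contacted | Subject left out | L | p | Subject included | L | p |
|---|---|---|---|---|---|---|
| 60 | 59/59 | 0.9505 | 0.0485 | 59/60 | 0.9234 | 0.192 |
| 61 | 60/60 | 0.9513 | 0.0461 | 60/61 | 0.9246 | 0.184 |
| 65 | 64/64 | 0.9543 | 0.0375 | 64/65 | 0.9291 | 0.158 |

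Every row passes with the subject left out and fails with the subject included. As a check on the 60/61 row: p = 0.95^61 + 61 × 0.05 × 0.95^60 = 0.0438 + 0.1405 = 0.184.

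**Tolerance of the test.** The smallest n that passes with no event is 59 (58/58 gives 0.9497). The smallest that passes with one event is 93 (92/93 gives 0.95001; 91/92 gives 0.9495), well above the cap of 65. At every n from 59 to 65 the test passes only with zero events.

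**The case against.** Several objections have force.

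- **The passages can be reconciled.** Section 6.4 sets an enrolment target and 11.5 sets analysis sets; these need not match. Section 11.7 mainly gives timing, and the secondary population in 10.2 may be a slip for the sensitivity population. This is fair, but it leads to the reading that omits contacted subjects, so it does not remove the problem.
- **The chain is long.** The failure must be labelled patient factors, the same subject must have a severe complication that did not cause the failure, and no one else may have an event. The first limb of 10.1.6 needs four conditions together. The second limb, however, counts any serious adverse event, with no relatedness condition. The documents give no rate for any link.
- **The event stays visible.** It would be recorded (10.2), assessed if serious (10.3) and shown in the sensitivity analysis (11.5). That is so; it is only outside the deciding test.

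Some stronger readings are tempting but not supported:

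- A reader might infer that the primary test shares the defect. Its population is prespecified, an intent-to-treat comparison is planned in 11.5, and 11.7 adds an all-subjects analysis. No change is needed there.
- A reader might call this the only formal safety test. The primary endpoint is itself a tested composite of safety and effectiveness.
- A reader might expect exclusions alone to sink the test, since 58/58 fails. Section 6.6 allows replacement if timelines permit, and with all 65 places used, six exclusions leave 59/59, which passes.
- A reader might think it unclear whether the test would be run at all: "If the enrolment target is not reached, the exact confidence interval will be calculated for the data available, but no hypothesis test" will be done. But 6.4 already defines the secondary enrolment target by contact.
- A reader might infer that subjects who withdraw after contact are dropped, because those who "withdraw from the study prior to being catheterized with the investigational device, will be excluded from analysis". The reason given, "The justification being they were never touched, and no measurements were made with the investigational device", indicates that touched subjects are not meant. The wording could be tighter, but the point is thin.

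**Conclusion.** The concern holds in a limited form. The secondary test's population is not named where the test is defined, and the likelier reading excludes some device-exposed subjects. The gap is confined to a severe complication, under either limb of 10.1.6, in a contacted patient-factor failure that the complication did not cause. Given one such subject, no other event and at least 59 subjects in the primary population, the conclusion changes from pass to fail at any sample size up to the cap. How likely this is cannot be computed from the documents. It would also be wrong to infer that a severe complication could go unreported; the plan's recording and reporting rules exclude that. The matter should be fixed because the test has no tolerance for events and the correction is small.

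**What to change.** In 11.5, define the population for the secondary test as every enrolled subject in whom the investigational catheter made contact, whatever the reason for a failed catheterization and regardless of later withdrawal. Make 10.2, 11.2 and 11.7 refer to it, and state that the 60-subject target in 11.2.2 is counted on the same basis as in 6.4. Leave the primary analysis population as it is.

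The cost is wording in four sections. No extra subjects are needed, because 6.4 already requires 60 with contact. The case report forms are not among the documents, so the sponsor should confirm that they capture contact and the reason for failure. The downside for the sponsor is that a severe complication in a subject whose catheter was never placed would count against the test.

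### Section 11.5 excludes withdrawals before catheterization, but its reason covers only subjects the device never touched; a subject who withdraws during insertion can fall out of both analysis populations

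*Combined protocol and SAP*

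**What the plan says.** Section 11.5 (Analysis Population) sets four rules.

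- The primary analysis population "will include enrolled subjects who have been successfully catheterized using the investigational device".
- Failed insertions attributable to the device or to an event are kept: "Should catheterization fail due to a device deficiency, and/or adverse event, these subjects will still be included in the primary analysis".
- If insertion fails because of patient factors (anatomy, need for a coudé tip, wrong French size), "these subjects will be considered as part of the sensitivity analysis population". The section also calls this the intent-to-treat population and uses it for comparison only.
- Enrolled subjects who, whatever the reason, "withdraw from the study prior to being catheterized with the investigational device, will be excluded from analysis". The reason follows at once: "The justification being they were never touched, and no measurements were made with the investigational device".

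Three other sections bear on this. Section 6.4 makes signed consent the point of enrolment. It sets the recruitment target by attempts ("the target enrolment is a minimum of 30 subjects with an attempted UDS study") and defines an attempt as the catheter having made contact with the patient's body. Section 6.6 allows withdrawn subjects to be replaced if timelines permit, but not because of poor results, and asks for the reason for withdrawal where possible. Section 11.1.1 classifies a procedure as a failure unless the clinician judges the device both safe and effective.

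**The concern.** The withdrawal rule and its justification describe different sets of subjects. The rule applies up to the moment of catheterization and regardless of reason. The justification applies only where there was no contact. Between them is the subject in whom insertion was started and who then withdraws. That subject was touched, counts as an attempt under Section 6.4, and was not successfully catheterized.

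Two things are left open. If the insertion failed because of an adverse event or device deficiency and the subject also withdrew, one rule retains the subject and the other excludes the subject, and neither is given precedence. If no adverse event or deficiency was recorded and none of the listed patient factors applies, only the withdrawal rule is left.

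Difficulty at insertion is one of the ways a redesigned catheter can fall short. The study is open label, the investigator rates the endpoint, and Section 3.6 describes temporary discomfort on insertion as something subjects may experience. A site could therefore record a withdrawal with no adverse event attached. Excluding such subjects can only raise the observed success rate if they would otherwise be failures, and the sensitivity analysis would not show it because the same rule removes them there.

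**Working it through.** **Inputs.** From Sections 11.1.1 and 11.1.2: null rate 75%, assumed true rate 96%, one-sided type I error 2.5%, n = 30, lower limit of the two-sided 95% Clopper-Pearson interval, stated power 88%.

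**Reproducing the plan's figure.** For x successes in n, the lower limit is the 0.025 quantile of Beta(x, n − x + 1). At n = 30:

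- 28/30 gives 77.9%, above 75%, a pass.
- 27/30 gives 73.5%, a fail.

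So the rule is at least 28 successes, that is, at most 2 failures. Power is P(X ≥ 28 | n = 30, p = 0.96) = 0.883, which agrees with the stated 88%. The attained type I error is P(X ≥ 28 | n = 30, p = 0.75) = 0.0106.

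**One subject, excluded or counted.** Take 30 contacted subjects with 27 successes and 3 failures, one failure being a withdrawal during insertion.

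- Counted: 27/30, lower limit 73.5%, fail.
- Excluded: 27/29, lower limit 77.2%, pass.
- Excluded and replaced by a success: 28/30, lower limit 77.9%, pass.

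**How many omitted failures would undo a pass.** Add k omitted failures to 30 analysed subjects:

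| Analysed | Last total that passes | First total that fails | k at first fail |
|---|---|---|---|
| 28/30 | 28/30 (77.9%) | 28/31 (74.2%, p = 0.031) | 1 |
| 29/30 | 29/31 (78.6%) | 29/32 (74.98%, p = 0.0252) | 2 |
| 30/30 | 30/33 (75.7%) | 30/34 (72.5%, p = 0.049) | 4 |

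**Effect on the false-pass chance.** The documents give no rate of withdrawal during insertion, so this is a range of assumptions. Let f be the fraction of all attempts that are failures, lost by this route and replaced so that 30 are still analysed. With a true per-attempt rate of 75%, the apparent rate is 0.75/(1 − f), and the false-pass chance is P(X ≥ 28 | n = 30) at that rate. Because failures are 25% of attempts, f/0.25 is the share of failures lost.

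| f | Share of failures lost | Apparent rate | False-pass chance |
|---|---|---|---|
| 0 | 0 | 75.0% | 1.1% |
| 2% | 8% | 76.5% | 1.7% |
| 5% | 20% | 78.9% | 3.3% |
| 10% | 40% | 83.3% | 10.3% |

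The nominal 2.5% is exceeded somewhere between f = 2% and f = 5%.

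**Secondary endpoint.** With the one-sided 95% limit and a 95% target (Section 11.2.1), 60/60 passes (95.1%) and 59/60 fails (92.3%). Dropping contacted subjects without an event shrinks this denominator and makes the target harder to meet. There is no favourable bias from that, but the denominator should still be every subject exposed to the device.

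**The case against.** A reader might infer that Section 11.5 removes device-caused failures even from the intent-to-treat analysis. The documents do not support that. The same section expressly keeps insertions that fail through a device deficiency or adverse event in the primary analysis. Section 10.1.1 defines an adverse event as any untoward medical occurrence, Section 3.6 names pain and urethral trauma as risks, and Section 10.1.3 includes inadequate performance and use errors among device deficiencies. A painful or device-caused failure that is recorded as such therefore has a strong claim to be retained. The stated reason, "they were never touched, and no measurements were made with the investigational device", also favours reading the exclusion narrowly.

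Other points count against a strong reading. Asking to stop an insertion is not the same as withdrawing from the study; a subject who only stops can still be rated and followed up. Section 6.6 bars replacement because of poor results, so the replacement scenario needs a withdrawal that is not seen as a poor result. It also already asks for the reason for withdrawal where possible.

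A remedy that made every withdrawal after pain or an insertion problem an automatic failure would go too far. It would override the clinician's rating in Section 11.1.1 and could clash with the patient-factor rule.

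All of this stands, and it narrows the point. It does not settle which rule prevails when a subject meets both, and it gives no place to the subject who withdraws after contact with no adverse event, deficiency or listed patient factor recorded.

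**Conclusion.** The point holds as a mismatch in the population rule. The exclusion is wider than its own justification, departs from the contact definition in Section 6.4, and has no stated precedence against the retention rule. The subjects exposed are those who withdraw from the study after contact and before successful catheterization. Those with no other classification recorded can leave both populations on a literal reading; those with an adverse event or deficiency recorded are subject to two opposing rules.

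The number affected may be small or zero. The consequence could still be decisive: with 2 failures allowed in 30, one subject can move the result from fail to pass, and between 1 and 4 omitted failures would undo a pass, depending on the count observed. The false-pass figures of 1.7%, 3.3% and 10.3% rest on assumed loss rates of 2%, 5% and 10% of attempts, with all lost subjects being failures and all replaced. They show sensitivity and do not forecast what will happen. At the lowest of these rates the error stays below the nominal 2.5%.

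**What to change.** In Section 11.5:

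1. Change the trigger for exclusion from catheterization to contact, so that it covers only subjects who withdraw before the investigational catheter made contact with the subject's body. This matches Section 6.4 and the sponsor's own reason, and untouched subjects stay excluded.
2. State that any subject who withdraws after contact stays in the sensitivity (intent-to-treat) population and in the secondary safety denominator.
3. State that the rule retaining failures due to a device deficiency or adverse event takes precedence over the withdrawal rule.
4. For the primary analysis, include post-contact withdrawals unless the existing patient-factor rule applies, and score them by Section 11.1.1: failure unless the clinician rates the device both safe and effective.

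On CRF 1, record whether withdrawal came before or after contact; Section 6.6 already asks for the reason where possible.

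The cost is a few sentences in Section 11.5 and one CRF item, with no added subjects or procedures. The downside is that the reported success rate may be slightly lower.
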